# 11.0 Privacy/Confidentiality Issues

During this study every attempt will be made to keep the patient's protected health information (PHI) private. Most study data will be maintained in a Vanderbilt REDCap database. Vanderbilt Redcap is a secure, web-based application for building and managing online databases. The data obtained and stored in Redcap will only be accessible by research personnel. Participating site, Texas Scottish Rite Hospital for Children, will be provided with access to the Vanderbilt REDCap database. The participating site will be able to view their records in the database but will not be able to view Vanderbilt's records. Any data sent to non-key study personnel for statistical analysis will be de-identified (dates will be shifted using a Redcap feature). Study personnel will use VUMC Box to share research documents. The VUMC Box study folder will only be accessible by research personnel. Any physical study forms (ex. consent documents, case report forms) will be kept in a locked cabinet in the principal investigator's office. All study data will be maintained for 6 years following study completion. Following this 6-year period, the Redcap database will be archived and all physical study forms will be disposed of in shred-it confidentiality bins provided by VUMC.

# 12.0 Follow-up and Record Retention

The duration of this study will last until we have enrolled and completed follow-up on 24 patients per group (N=48). All study data will be maintained for 6 years following study completion. Following this 6 year period, the Redcap database will be archived and all physical study forms will be disposed of in shred-it confidentiality bins provided by VUMC.

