# 5.0 Enrollment/Randomization

#### **Enrollment**

General inclusion/exclusion criteria will be used to determine patient eligibility for this study. Potential study participants will be identified when they present to the Vanderbilt Children's Orthopaedic or Texas Scottish Rite Hospital for Children clinics for treatment of presumed congenital idiopathic clubfoot.

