#### **Electronic Consent Process:**

In the event a potential study candidate is missed during a clinic visit, or research personnel are unavailable to consent in-person, study personnel will contact the patient's parent(s)/legal guardian(s) by phone to notify them of their child's study eligibility and ask if they would be interested in their child taking part. If the parent(s)/legal guardian(s) are interested in their child taking part in the study, study personnel will send a link to the REDCap-based electronic consent form by e-mail. If the parent(s)/legal guardian(s) agree for their child to take part in the study after reading the informed consent document, there will be an option for one parent/legal guardian to electronically sign their name and date the informed consent document. Once they electronically sign the electronic informed consent document, they will be given an option to save or print the signed electronic informed consent documents for their files.

We will seek to enroll 47 patients per group, 94 patients total in this study at each site.

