# 10.0 Statistical Considerations

# **Power Analysis**

A power analysis was conducted to determine the sample size needed to find a clinically meaningful difference of 2.5 point in the FLACC score (SD=3) between the two methods. With alpha=0.05, power=0.8, and and effect size d=.83, at least 24 patients per group are required (N=48). Assuming a 20% participant lost to follow-up rate, we will need to enroll 29 patients per group (N=58).

An interim power analysis was conducted to determine the sample size to find a clinically meaningful difference of 2.0 points in the FLACC score between the two methods. This was performed using the maximum SD of the FLACC score observations of the first 39 patients (SD=4.13). With alpha=0.05 and power=0.8, at least 47 patients per group are required (N=94).

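### Three sample sizes stand in the current text (48, 94, and 94 per site), none is named as governing, and 94 in total gives about 64% power, not the stated 80%

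*Combined protocol and SAP*

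**What the plan says.** Three sections give a number of patients.

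- Section 12.0 (Follow-up and Record Retention) sets the end of the study: "The duration of this study will last until we have enrolled and completed follow-up on 24 patients per group (N=48").
- Section 10.0 (Power Analysis) first derives 24 per group for a "clinically meaningful difference of 2.5 point in the FLACC score (SD=3) between the two methods", then adds a loss allowance: "Assuming a 20% participant lost to follow-up rate, we will need to enroll 29 patients per group (N=58"). It next reports an interim recalculation for a difference of 2.0 points. On the SD it says: "This was performed using the maximum SD of the FLACC score observations of the first 39 patients (SD=4.13"). The result is: "With alpha=0.05 and power=0.8, at least 47 patients per group are required (N=94").
- Section 5.0 (end of the Electronic Consent Process text) sets the enrolment target: "We will seek to enroll 47 patients per group, 94 patients total in this study at each site". The same section names two places of recruitment, the "Vanderbilt Children's Orthopaedic or Texas Scottish Rite Hospital for Children clinics".

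All of this is current text, not an amendment log. Nothing in it says that one figure replaces another.

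**The concern.** The three statements cannot all hold. Section 12.0 repeats the original requirement, section 10.0 moves to 94, and section 5.0 can be read as 94 overall or as 94 at each of two clinics (2 × 94 = 188). Someone applying section 12.0 literally would close the study at about half the recalculated size.

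The natural repair is to copy section 10.0's figure into the other two sections. That works only if 47 per group delivers the power claimed for it. If it does not, the repair spreads an unsupported 80% claim through the protocol.

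It is also unclear what 94 counts. The original calculation separates the number required (24 per group) from the number to enrol (29 per group). In the recalculation, section 10.0 calls 47 the number required and section 5.0 calls 47 the number to enrol, so no allowance for loss is left.

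**Working it through.** **Inputs**

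- Original calculation (section 10.0): difference 2.5, SD 3, alpha 0.05, power 0.80, 24 per group.
- Interim calculation (section 10.0): difference 2.0, SD 4.13, alpha 0.05, power 0.80, 47 per group.
- Allocation 1:1 (section 5.0, Randomization).
- Loss 20% (section 10.0, original calculation only).
- Assumption: a single unadjusted two-sample t-test. Section 10.0 names neither the test nor its sidedness.

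**Formulas**

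Standardised difference d = difference / SD. Normal approximation: n per group = 2 × (1.960 + 0.842)² / d². Exact power uses the noncentral t distribution with 2n − 2 degrees of freedom and noncentrality d × √(n/2).

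**Step 1: reproduce the original 24.** d = 2.5/3 = 0.833. The approximation gives 2 × 7.849 / 0.694 = 22.6, so 23. The t-test gives 23.6, so 24, with 80.7% power. The plan's figure is reproduced. A one-sided test would need only 19, so the plan's own convention is two-sided.

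**Step 2: try to reproduce 47.** d = 2.0/4.13 = 0.484. The approximation gives 2 × 7.849 / 0.2345 = 66.9, so 67. The t-test gives 67.9, so 68 per group (N=136). The figure of 47 is not reproduced.

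**Step 3: power at each candidate size** (2.0 points, SD 4.13, t-test, alpha 0.05)

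| Per group | Total | Two-sided | One-sided |
|---|---|---|---|
| 24 | 48 | 37.6% | 50.3% |
| 47 | 94 | 64.2% | 75.3% |
| 68 | 136 | 80.05% | 87.8% |
| 94 | 188 | 91.0% | 95.2% |

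Hand check at 47: the noncentrality is 0.484 × √23.5 = 2.35, and Φ(2.35 − 1.96) = Φ(0.39), about 65%. A one-sided test would need 54 per group, so sidedness does not explain 47.

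**Step 4: what 47 per group does support.** 80% two-sided power needs d = 0.584. That is 0.584 × 4.13 = 2.41 points at the interim SD, or an SD of 2.0/0.584 = 3.42 for 2.0 points.

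**Step 5: range at N=48.** Power is 81% for 2.5 points at SD 3, 62% for 2.0 points at SD 3, 54% for 2.5 points at SD 4.13, and 38% for 2.0 points at SD 4.13.

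**Step 6: loss.** If 47 counts enrolled infants and 20% are lost, 47 × 0.8 = 37.6 remain per group. Power is then 53.8% at 37 and 54.9% at 38. In the other direction, 47/0.8 = 58.75, so 59 per group (118), and 68/0.8 = 85 per group (170). The plan's own 29 comes from multiplying (24 × 1.2 = 28.8). That method would give 57 and 82 here, but multiplying leaves slightly too few after a 20% loss.

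**Where 47 may have come from (inference only).** With 2.0 points and the old SD of 3, the t-test needs 37 per group, and 37/0.8 = 46.25 rounds up to 47. The documents do not say this was done.

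**The case against.** The strongest reply is that the intended number is plain enough. Sections 5.0 and 10.0 agree on 47 per group, section 10.0 runs in order from the original to the interim calculation, and N=48 sits in a record-retention section. This has force: 48 is very likely a remnant, and the live question is mainly 94 against 188. But no passage retires 48, and on the 94-or-188 question the text gives no answer. The power shortfall applies only if 94 is the trial total; at 188, power exceeds 80%.

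A second reply is that the t-test is not the planned analysis. The Data Analysis text plans a repeated-measures ANOVA on changes, with Sidak comparisons at 10 time points, and SD 4.13 is the largest SD observed, hence cautious. Baseline adjustment with a correlation of about 0.56 (an assumed value) would bring 47 per group to about 80%. Section 10.0 states no correlation and no adjustment, so this cannot support its claim. The multiplicity correction pulls the other way. At the Sidak level for 10 comparisons, 1 − 0.95^(1/10) = 0.0051, power for one time point is about 31% at 47 per group and about 49% at 68. The 64% is therefore not a bound in either direction, and 136 would not secure 80% for each corrected comparison.

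A third reply is that 20% loss is pessimistic. Randomisation comes on or after the final casting visit, and procedural FLACC is recorded on the day of tenotomy, so few randomised infants should lack it. That is fair. The 54–55% figure is a low-end scenario, and it depends on what 94 counts, which the plan does not say.

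**Conclusion.** The concern holds, and the protocol should be corrected. The current text carries totals of 48, 94 and possibly 188 with no statement of which governs, and the only sentence defining the end of the study uses the smallest. Separately, 47 per group does not follow from 2.0 points, SD 4.13, alpha 0.05 and 80% power. If 94 is the trial total, power on those inputs is about 64% two-sided or 75% one-sided, and 80% needs 68 per group two-sided or 54 one-sided.

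These figures rest on a single unadjusted t-test with equal groups and no loss. Two-sidedness is inferred from the original 24, which is reproduced only that way. The conflict between sections does not depend on any of these assumptions.

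**What to change.** Make one amendment to three sections.

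- **Section 12.0:** delete the 24 per group (N=48) and refer to the total in section 10.0.
- **Section 5.0:** replace the per-site wording with the intended total across both sites.
- **Section 10.0:** redo and document the interim calculation, naming the test and its sidedness. State whether the total counts enrolled, randomised or evaluable infants, and whether the 20% allowance still applies.

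The least costly version keeps 94 evaluable infants in total, stated as about 64% power for 2.0 points at SD 4.13, or 80% for about 2.4 points. It adds no evaluable infants. If 80% power for 2.0 points is to be kept, the total is 136 evaluable, which is 136 − 94 = 42 more, with the caveat that this is for one uncorrected comparison. If 94 per site was meant, state 188 and about 91% power. With the 20% allowance (dividing by 0.8), enrolment would be 118 for 94 evaluable or 170 for 136. The choice is the sponsor's, but the same figure and its matching power must appear in all three sections.

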#### 14.0 Temperament Assessment Evidence

"The Origin of Personality" by Thomas, Chess and Birch, 1970.

- "Infants begin to express themselves as individuals from the time of birth."
- "[Thomas, Chess, & Birch] identified nine characteristics that could be reliably scored on a three point scale (medium, high and low). The set of ratings in these nine characteristics defines the temperament, or behavioral profile, of a child, and the profile is discernible even as early as the age of two or three months."
- "Children do show distinct individuality in temperament in the first weeks of life, independently of their parents' handling or personality style. Our long term study has now established that the original characteristics of temperament tend to persist in most children over the years."

- "[Thomas, Chess, & Birch] found that certain characteristics did cluster together and defined three general types of temperament: easy, difficult, and slow to warm up."
- "Behavior of a child reveals that he has a distinct temperament early in life. These reports taken from interviews with the parents of the children studied by the authors show that temperamental differences are apparent when a child is only two months old."
- Temperamental characteristics that are crucial to classifying a child as easy, slow to warm up, and difficult are rhythmicity, approach/ withdrawal, adaptability, intensity of reaction, and quality of mood." ((we also included threshold of responsiveness))
- \*\*We will take 6 of the 9 characteristic stages, including each of the 5 crucial characteristics, for our study. Results will be broken into subgroups

